Date: 1 March 2020

Study Name: Comparison Of The Incidence Of Recurrent Laryngeal Injury Following The Dissection Of The Nerve By Cranio-Caudal And Lateral Approach By Using Introoperative Nerve Monitoring

Study Design: This prospective study was approved by the institutional review board and informed consent was obtained from each patient . A total of 327 patients who were referred to undergo thyroid surgery between June 2018 and November 2019 were assessed for the eligibility to participate in the study. Of these, 233 were considered to be eligible for the study. Exclusion criteria included previous thyroid or parathyroid surgery, substernal goiter, preoperative VCP, evidence of lateral lymph node metastasis, intentional transection of the RLN due to tumor invasion, failure to assess RLN functioning due to equipment issues with the IONM setup, presurgical dissection amplitude of $<500\mu\text{V}$ and patient's refusal to participate in the study. Of 327 patients, 94 were excluded preoperatively due to previous neck surgery (n=47), evidence of lateral neck metastasis(n=24), patient's refusal (n=13) and presence of substernal goiter (n=10). The remaining 233 patients were randomized to have RLN's identified by lateral (n=121) or cranio-caudal approach (n=112 (Figure 1). Computer generated random numbers were generated and printed on cards. These cards were placed in sealed, opaque envelopes. On the morning of operation, one envelope was opened before the operation and, depending of the parity of the number, RLN's of the patient were dissected either by cranio-caudal or lateral dissection during the operation. The patients and the nerves at risk (NAR's) in the lateral and cranio-caudal approach groups were classified as group 1 and 2, respectively. In group 1 and 2, nine and twenty-six patients were further excluded, respectively, owing to intraoperative failure to assess RLN functioning due to equipment issues with the IONM setup or presurgical dissection amplitude of $<500\mu\text{V}$.

Thus, the data of 198 patients were analysed for primary and secondary outcome measures. The primary endpoint was RLN injury and the secondary endpoints included the effect of clinicopathological features, anatomic variations and adverse EMG changes on the occurrence of RLN injury. Of 198 patients, 112 were in the lateral approach group (group 1) and 86 in the cranio-caudal approach group (group 2). Total thyroidectomy or lobectomy was

performed in 158 (79.8%) and 40 (20.2%) patients, respectively. Sixteen (8%) patients underwent unilateral central lymph node dissection (CLND) additional to total thyroidectomy. Age, gender, body mass index (BMI), the indications for surgery, presence of hyperthyroidism, evidence of autoimmune thyroid disease (ATD) and thyroid lobe volume were recorded in all patients, preoperatively. Thyroid lobe volume was calculated by using the dimensions (length(L), width(W), thickness(T)) of each thyroid lobe measured by ultrasonography according to the following formula; $\pi/6 \times L \times W \times T^{18}$.

All NAR's were dissected by using CIONM including vagal response evaluation at the beginning and at the end of the operation (IONM = L1,V1, R1, R2,V2, L2) according to the recommendations by the International Intraoperative Neural Monitoring Study Group ⁷. All patients underwent pre-, and postoperative laryngoscopic examination within 2 days after surgery, and repeated serially if abnormal (L1, L2). All operations were performed by experienced endocrine surgeons. Length of RLN dissection was defined as extended if the nerve was dissected for 5 cm or greater. Duration of lobectomy for each site, period of time for initial identification of RLN after the mobilization of upper pole on each site, the relationship of the RLN to the ligament of Berry (LOB) and to the Tubercl of Zuckerkandl (TZ) (if present), extralaryngeal branching of the RLN, length of RLN dissection, presurgery and postsurgery amplitude and latency of the vagus and the RLN, occurrence of adverse EMG changes and recovery time or loss of signal (LOS) were recorded intraoperatively in all patients. Serum levels of calcium and parathormone on the first postoperative day were analyzed in all patients. The rates of post-thyroidectomy hypoparathyroidism and vocal cord palsy (VCP) were recorded. Final histopathological diagnosis was documented in all patients, postoperatively.

Demographic data, BMI, the indications for surgery, clinicopathological features, thyroid volume, duration of the operation, period of time for RLN identification, anatomical variations, length of RLN dissection, presurgery and postsurgery amplitude and latency of the vagus and RLN, the rate of adverse EMG changes, LOS and morbidity (vocal cord palsy, hypoparathyroidism) were compared between group 1 and 2. The correlation between intraoperative adverse EMG changes and anatomic variations, lobe volume and type of thyroid disease was investigated as well.

Thyroid surgery and CIONM technique

All operations were performed under general anesthesia by using a small dose (0.3 mg/kg) of non-depolarizing muscle relaxant (Esmeron; MSD Sharp & Dohme GmbH, Haar, Germany) at intubation. The endotracheal tube was properly inserted to ensure that the recording surface electrode was placed at the level of the vocal cords. Prior to lobectomy, the carotid sheath was carefully dissected and the vagus nerve was identified using a hand held stimulation probe. The vagus nerve was dissected over a distance of ≤ 1 cm to place the vagus electrode. (automated periodic stimulation (APS) (Medtronic Xomed, Jacksonville, FL) or saxaphone probe (vagus electrode) ([name] GmbH, Avalanche SI, Germany).

The baselines for latency and amplitude were automatically calibrated after the connection of the vagus electrode with the neuromonitoring system. CIONM had been carried out with one of the two following commercially available neuromonitoring devices: (1) NIM 3.0 Nerve Monitoring Systems; Medtronic Xomed, Jacksonville, FL; or (2) [name] GmbH, Avalanche SI, Germany. Achievement of initial presurgical dissection amplitude of $\geq 500\mu\text{V}$ was aimed in all patients. During the operations, adverse EMG parameters were defined as amplitude decrease of 50% or more of baseline value and/or latency increase of 10% or more ¹¹. A combined event (CE) was defined as concordant amplitude decrease of more than 50% and latency increase of more than 10%, regarding to baseline values ¹¹. The surgical maneuver was immediately altered and the traction released if adverse EMG changes were noted during surgery and waited to achieve the recovery of EMG changes. Recovery was defined as amplitude recovery to $>50\%$ of the initial baseline amplitude. Loss of signal (LOS) was defined as amplitude $<100\mu\text{V}$ ¹⁹. In case of LOS during the surgery of initial site, contralateral surgery was aborted if the amplitude did not recover to greater than 50% of the initial baseline amplitude within 20 minutes of the initial decline. During surgery, isthmus was divided first in both group of patients. Then the upper lobe of the gland was dissected through the avascular zone between the upper lobe and the cricothyroid muscle. The external branch of the superior laryngeal nerve was identified visually and, or by using neuro-monitoring hand probe prior to dissection of the upper pole vessels, and then the branches of upper pole vessels were ligated individually. Identification and preservation of all parathyroid glands and their vascular supply was tried in all cases. In case of incidental parathyroidectomy or totally compromised vascularity of the parathyroid glands, autotransplantation in to sternocleidomastoid muscle was performed.

RLN identification

Lateral approach: Following the ligation of upper pole vessels, the thyroid lobe was pulled anteromedially and the RLN was seeked within the carotid triangle at the level of inferior thyroid artery (ITA). The tissue between the carotid artery and the trachea was dissected gently parallel to the direction of the nerve until the nerve is identified visually and by hand held stimulation probe. After the identification of RLN, the vessels of inferior thyroid lobe was ligated. The nerve was dissected along its course to the entry point, and then the thyroid lobe was totally dissected from the trachea and the lobectomy was completed. If adverse EMG changes were encountered during lateral approach, traction was released immediately and waited for recovery. If the adverse EMG changes recovered, RLN dissection was proceeded by lateral approach again. If the adverse EMG changes did not recover after traction release or in case of repeated adverse EMG changes, lateral approach was abandoned. The thyroid lobe was retracted laterally and medial aspect of the lobe was dissected from the trachea. The RLN dissection was continued by medial approach in such cases.

Cranio-caudal approach: Following the ligation of upper pole vesels, the upper pole was retracted antero-medially to expose crico-pharyngeal muscle. The RLN was identified at the point of entry both visually and with hand held stimulation probe. The RLN dissection was proceeded craniocaudally by the division of the suspensory ligaments of the LOB through the level of ITA. After the identification and visualization of the RLN through its whole course, the medial and inferior vessels of the thyroid gland were dissected and ligated. Then, the lobe was dissected from the trachea and lobectomy was completed. If adverse EMG changes were encountered during cranio-caudal approach, traction was released immediately and waited for recovery. The RLN dissection was proceeded by cranio-caudal fashion again if the EMG changes recovered. If the EMG changes did not recover or in case of repeated adverse EMG changes, cranio-caudal approach was abandoned and RLN was dissected by lateral approach. If repeated adverse EMG changes were encountered despite conversion from cranio-caudal to lateral approach, then the lobe was retracted laterally and medial aspect of the lobe was dissected from the trachea. The RLN was dissected by medial approach in such cases with repeated adverse EMG changes.

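### The plan does not say whether side-level outcomes are analysed per patient or per nerve, and its tests make no allowance for two nerves from one patient

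*Protocol*

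**What the plan says.** Randomisation is by patient (Protocol, Study Design): after the envelope is opened, "RLN's of the patient were dissected either by cranio-caudal or lateral dissection during the operation". The same section then names two units: "The patients and the nerves at risk (NAR's) in the lateral and cranio-caudal approach groups were classified as group 1 and 2, respectively". The analysis set is given as a count of patients: "Thus, the data of 198 patients were analysed for primary and secondary outcome measures". The primary endpoint is RLN injury, not defined as per nerve or as any nerve in a patient. Of the secondary endpoints the protocol says "the secondary endpoints included the effect of clinicopathological features, anatomic variations and adverse EMG changes on the occurrence of RLN injury".

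Total thyroidectomy or lobectomy was "performed in 158 (79.8%) and 40 (20.2%) patients, respectively". Some measures are explicitly taken by side, for example "period of time for initial identification of RLN after the mobilization of upper pole on each site". The list of variables compared between groups 1 and 2 includes "period of time for RLN identification, anatomical variations, length of RLN dissection, presurgery and postsurgery amplitude and latency of the vagus and RLN", as well as adverse EMG changes and loss of signal (LOS). These stand beside patient-level items such as BMI and hypoparathyroidism. Laryngoscopy is described by patient: "All patients underwent pre-, and postoperative laryngoscopic examination within 2 days after surgery".

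The SAP names the t-test, Mann-Whitney, chi-square, and a logistic regression fed by significant univariate results at p<0.05. It gives no unit of analysis, no rule for reducing two sides to one value, and no method for within-patient correlation. Under Thyroid surgery and CIONM technique, the protocol adds that unrecovered LOS on the first side cancels surgery on the second.

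**The concern.** A patient's two nerves share the operation, the assigned approach and the patient's own anatomy and disease, so their outcomes may be alike. Entering both as independent observations overstates the information on anything constant within a patient: the arm, age, BMI, thyroid disease. P-values are then too small and confidence intervals too narrow. The p<0.05 screen carries the error forward, because patient-level predictors would enter the logistic model on the strength of those tests.

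The question also arises if the patient is the unit. A patient with two identification times or two amplitudes needs a stated rule (mean, worse side, first side), and RLN injury needs one too (any nerve injured). Without it, the choice can be made after the data are seen.

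**Working it through.** **Inputs from the protocol.** 121 and 112 patients randomised; 9 and 26 excluded afterwards; 158 total thyroidectomies and 40 lobectomies. Significance level 0.05 (SAP), taken as two-sided because sidedness is not stated. The intraclass correlation (ICC), injury risk and share of first-side events that abort the second side are not in the documents and are assumed below.

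**1. Patient flow.** 121 − 9 = 112; 112 − 26 = 86; 112 + 86 = 198 = 158 + 40; 158/198 = 79.8%. The protocol's figures reproduce.

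**2. Nerve count (derived, not stated).** 2 × 158 + 40 = 356. This takes the operation performed as the one planned; if aborted cases were recorded as lobectomies, 356 is the actual count.

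**3. Design effect.** Size-weighted mean cluster size = (158 × 4 + 40 × 1)/356 = 672/356 = 1.888. Design effect DE = 1 + 0.888 × ICC. Effective nerves = 356/DE. True alpha = 2 × (1 − Φ(1.96/√DE)). Correct confidence intervals are wider by √DE − 1.

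| Assumed ICC | DE | Effective nerves | True alpha | Interval widening |
|---|---|---|---|---|
| 0 | 1.00 | 356 | 5.0% | 0% |
| 0.05 | 1.04 | 341 | 5.5% | 2% |
| 0.1 | 1.09 | 327 | 6.0% | 4% |
| 0.3 | 1.27 | 281 | 8.2% | 13% |
| 0.5 | 1.44 | 247 | 10.3% | 20% |

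Simulation with 112 and 86 patients and no arm effect agrees. At ICC 0.1, 0.3 and 0.5 the nerve-level t-test rejected in 6.1, 8.1 and 10.5% of runs and Mann-Whitney in 5.6, 8.1 and 10.1%. With patient-clustered standard errors or patient means, the rate was 4.7–5.2%.

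**4. Where the full effect applies.** Outcomes not tied to the abort rule: identification time, anatomy, dissection length and presurgery signals. For adverse EMG changes (assumed in 20% of nerves, a quarter of first-side events aborting), alpha was 5.8, 7.8 and 10.0% at ICC 0.1, 0.3 and 0.5.

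**5. RLN injury.** Uncorrected chi-square per nerve, assumed risk 2–10%, ICC 0.3–0.5:
- no first-side events abort: about 8–10.5%
- half abort: about 6.5–8%
- three quarters abort: about 6% (5.2–7.0% across simulations)
- all abort: about 5%

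For any injury per patient, chi-square alpha was about 4–6% and Fisher's exact 2.5–4.1%.

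**6. Predictors.** For a patient-level predictor present in 30% of patients, the uncorrected nerve-level test gave 3.9–11.1% and permutation across patients 3.8–5.8%. Predictors that vary by side (lobe volume, branching) are unaffected only if independent between sides (4.7–5.4%). If correlated between sides, alpha was about 3.5–8.5%, in either direction.

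**7. Denominator.** Write b = 158/198, s = share of first-side events that abort, p = true risk. The per-nerve rate is [p + b(p − s(p² + ICC × p(1 − p)))]/[1 + b(1 − s × p)]. At ICC 0.3, a true 5% against 10% shows as a 4.7-point difference with half aborting and 4.4 points with all aborting. The effect is small, but GEE does not remove it (4.30% and 8.63% in a large simulated sample with all aborting).

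**The case against.** The strongest reply is that the protocol's only sentence on the analysis set counts patients, that the intraoperative measures are said to be recorded in all patients, and that laryngoscopy is per patient. On that reading nothing is clustered. It is a plausible reading for RLN injury, and there the clustering objection falls away. It does not settle the side-level measures: a count of 198 patients does not say which value represents a patient who has two, and the protocol also assigns nerves to the groups.

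Second, the harm is doubly conditional, on nerve-level testing and on a positive ICC, and the documents establish neither. This stands. At ICC 0.05–0.1 alpha is only 5.5–6.0%; about 10% needs ICC 0.5.

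Third, the abort rule protects the primary endpoint. This is partly right. A reader might infer that alpha for per-nerve RLN injury stays near 5% once most first-side events abort. That holds only when nearly all abort or the ICC is low. The rule is triggered by unrecovered LOS, not by every injury, and the number of aborted second sides is not given.

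Fourth, arm comparisons of identification time, anatomy and presurgery signals are not listed as endpoints. This limits the severity.

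**Conclusion.** The gap is real: two units are in play, side-level data are compared between arms, and neither document states the unit, a combining rule or a method for paired sides. Confidence in this is high.

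The size of the distortion is held with moderate confidence. It rests on nerve-level testing and an assumed positive ICC: alpha about 5.5–10.3% over ICC 0.05–0.5 for outcomes not linked to the abort rule, less for RLN injury, and none at ICC 0.

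A reader might infer that the primary comparison is invalid, that 356 nerves were in fact analysed, or that every predictor's p-value is too small. The documents support none of these. RLN injury may have been counted per patient, 356 is derived, and predictors that differ between sides can err either way. This should be fixed, but it does not by itself overturn the primary result.

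**What to change.** State the unit for every outcome and predictor analysis, then:

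1. **Primary test.** Any RLN injury per patient (yes/no) by arm, with chi-square, or Fisher's exact test if events are few. State that this uses the 198 analysed patients, not all 233 randomised. Report or stratify by one versus two nerves at risk.
2. **Side-level outcomes and all nerve-level predictor models, including side-level predictors.** Use the patient mean for continuous outcomes, or patient-clustered robust standard errors or GEE. Where a category has few or no events, test arm and patient-level predictors by permuting labels across patients with both sides kept together. Clustered logistic regression is unreliable there: at 2% risk its simulated alpha was 0.4–1.3%, against 3.9–5.8% for permutation over risks of 2–10%.
3. **Aborted second sides.** Report their number by arm, since clustering methods do not correct the denominator.

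**Cost.** SAP wording and a re-run on existing data with a patient identifier, plus a look-up of aborted second sides in operation records. Nerve-level intervals widen by about 2–20% for ICC 0.05–0.5. The per-patient test loses about 0–4 points of nominal power against the uncorrected nerve-level test in the scenarios checked: 85–86% against 86% for an assumed 5% vs 15% per nerve, 82% against 85% with the arms reversed, and 31% against 35% for 2% vs 5%. Part of that gap is the uncorrected test's inflated alpha.

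### RLN injury was analysed only after 26/112 cranio-caudal and 9/121 lateral patients had been excluded post-randomisation, so the comparison is not protected by randomisation

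*Protocol*

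**What the plan says.** All of the following is in the protocol's Study Design section unless stated otherwise.

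- 233 patients were randomised by sealed envelope, 121 to the lateral approach (group 1) and 112 to the cranio-caudal approach (group 2).
- Allocation was revealed before surgery: "On the morning of operation, one envelope was opened before the operation".
- Exclusions followed: "In group 1 and 2, nine and twenty-six patients were further excluded, respectively, owing to intraoperative failure to assess RLN functioning". Two reasons are given together, IONM equipment problems and a presurgical amplitude below 500 µV. Both also stand in the list of exclusion criteria.
- The analysis set is what remained: "Thus, the data of 198 patients were analysed for primary and secondary outcome measures". The primary endpoint is RLN injury.
- Laryngoscopy is described without reference to monitoring: "All patients underwent pre-, and postoperative laryngoscopic examination within 2 days after surgery".

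The SAP plans t-tests or Mann-Whitney tests, chi-square tests, and a logistic regression restricted to factors significant in univariate analysis. Neither document describes an analysis of all randomised patients, a sensitivity analysis that includes the 35, or any other handling of them.

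**The concern.** Exclusion after randomisation is harmless only if it is unrelated to allocation, for instance when it is decided on pre-treatment data by someone who does not know the arm. Here the surgical team knew the approach from the morning of operation, no blinded exclusion decision is described, and the arms lost patients at a threefold different rate.

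A causal claim about the approach and nerve injury would then rest on a subset selected after allocation. The between-group comparisons ("Demographic data, BMI, the indications for surgery, clinicopathological features, thyroid volume, duration of the operation" and others) could reveal measured imbalance among the 198, and the regression could adjust for some of it. Neither can deal with unmeasured imbalance, and nothing planned bounds the effect of leaving out the 35.

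**Working it through.** **Patient flow (protocol, Study Design).** 327 − 94 = 233; 121 + 112 = 233; 121 − 9 = 112; 112 − 26 = 86; 112 + 86 = 198. The stated 198 is reproduced. The figure 112 occurs twice by coincidence: it is the number randomised to cranio-caudal and the number analysed in the lateral group.

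**Size of the loss.** Overall 35/233 = 15.0%. Lateral 9/121 = 7.44%; cranio-caudal 26/112 = 23.21%.

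- Difference: 23.21 − 7.44 = 15.78 points (from unrounded rates); ratio 3.1.
- Wald SE = √(0.0744 × 0.9256/121 + 0.2321 × 0.7679/112) = 0.0465, so the 95% CI is 15.78 ± 1.96 × 4.65 = 6.7 to 24.9 points. Newcombe's interval is 6.6 to 25.1.
- Fisher p = 0.00086; Pearson chi-square 11.34, p = 0.00076; continuity-corrected 10.14, p = 0.0015.
- Expected cranio-caudal exclusions at the lateral rate: 112 × 9/121 = 8.3. Observed 26, an excess of 17.7.
- The randomised split of 121:112 is compatible with 1:1 (exact p = 0.60), so most of the 112:86 imbalance arises at the exclusion step.

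**Order of steps.** Under Thyroid surgery and CIONM technique, the vagus electrode is placed before lobectomy and the baseline is calibrated on its connection. Under RLN identification, the arms diverge only after the upper-pole vessels are ligated. If the 500 µV criterion refers to that baseline, a low reading comes before any arm-specific exposure, and such exposure is then a plausible cause mainly of equipment failures. Exclusion decisions made with the arm known, a different mix of the two monitoring devices by arm or, improbably, chance also remain open.

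**How far the result could move.** Let *d* be the injury risk in excluded patients minus that in retained patients of the same arm. The all-randomised risk in an arm is the retained risk plus the excluded share times *d*. Hence, for cranio-caudal minus lateral,

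RD(233) − RD(198) = 0.232 × d_cc − 0.074 × d_lat.

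The documents give no value for *d*. Assumed values, for scale only:

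| d_cc | d_lat | Shift (points) |
|---|---|---|
| +10 | +10 | +1.6 |
| +20 | +20 | +3.2 |
| +10 | 0 | +2.3 |
| −10 | −10 | −1.6 |
| 0 | +10 | −0.7 |
| −10 | +10 | −3.1 |

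**Best- to worst-case width.** With m_cc and m_lat outcomes missing, the patient-level width is m_cc/112 + m_lat/121:

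- all missing (26, 9): 30.7 points;
- (13, 4): 14.9 points;
- (5, 2): 6.1 points.

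Per nerve, count two nerves for each of 158 total thyroidectomies and one for each of 40 lobectomies: 2 × 158 + 40 = 356 retained nerves. The extent of surgery by arm is not given. Retained cranio-caudal total thyroidectomies can number 86 − 40 = 46 up to 86, which gives 132 to 172 cranio-caudal nerves and, correspondingly, 224 to 184 lateral nerves. The 35 add 26 to 52 and 9 to 18 nerves.

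- Narrowest: 26/(172 + 26) + 9/(184 + 9) = 17.8 points.
- Widest: 52/(132 + 52) + 18/(224 + 18) = 35.7 points.

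These widths come from denominators alone and are not evidence of bias.

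**The case against.** The strongest defence is that both reasons are listed exclusion criteria, and that a low amplitude measured before dissection is a pre-treatment characteristic. Excluding on such a measurement need not bias the comparison if the decision is unaffected by allocation, and nothing in the documents says that knowledge of the arm influenced any exclusion. That last point stands: influence is possible, not shown. But the criteria could be applied only in theatre with the arm known, and a threefold difference with p of about 0.001 is hard to put down to chance.

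It can also be argued that the 500 µV reading may have been taken on the RLN itself, since presurgical amplitudes are recorded for both vagus and RLN. The nerve is first reached at a different place in each arm, so exposure could then have contributed to low readings. This is a fair limit on the order-of-steps reasoning. It does not help the 198-patient analysis, because exclusion would then depend on the approach.

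Third, the study compares approaches under monitoring: traction release, conversion and stopping before the second side all depend on EMG. An analysis of all 233 partly reflects surgery without usable monitoring and answers a somewhat different question. This stands, and is why the 198-patient set should be kept alongside.

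Finally, the 35 may lack outcome data. The laryngoscopy sentence follows counts that describe only the analysed patients ("performed in 158 (79.8%) and 40 (20.2%) patients, respectively", and 158 + 40 = 198), so its reference to all patients may not include them. This limits how complete the remedy can be; it does not alter the problem.

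**Conclusion.** The concern holds and needs correction before any causal claim is made. The primary comparison uses 198 of 233 randomised patients, selected after allocation was known, with a loss of 23.2% against 7.4% (difference 15.8 points, 95% CI 6.7 to 24.9). This rests only on counts stated in the protocol.

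What is established is loss of the protection given by randomisation, not a demonstrated bias. The available text gives no injury counts, no outcomes for the 35 and no split of them by reason, timing or device (Figure 1 could not be seen and may give some of this). The shifts depend on assumed risks and can take either sign.

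**What to change.** 1. Report RLN injury in all 233 patients by allocated arm (121 versus 112), labelled post hoc, and base any randomised causal claim on that result.
2. Define injury as vocal cord palsy on postoperative laryngoscopy, which needs no EMG signal, once the sponsor confirms that definition and the unit of analysis (patient or nerve at risk).
3. Give best- and worst-case bounds for any of the 35 without a laryngoscopy result.
4. Keep the 198 for EMG endpoints and as a labelled analysis of monitored patients.
5. Tabulate the 35 by arm, reason, timing and device, unless Figure 1 already does so.

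**Cost.** A search of 35 patients' records, a re-analysis and its reporting; no new patients or procedures. Both documents are dated 1 March 2020 and describe the analysis in the past tense, for patients "referred to undergo thyroid surgery between June 2018 and November 2019". A change of SAP wording alone would therefore not be enough. Some outcomes may not be recoverable, in which case the bounds in step 3 show what remains unknown.

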Date: 1 March 2020

Study Name: Comparison Of The Incidence Of Recurrent Laryngeal Injury Following The Dissection Of The Nerve By Cranio-Caudal And Lateral Approach By Using Introperative Nerve Monitoring

Statistical Analysis Plan: The Statistical Package for Social Sciences (SPSS) for Windows Version 21.0 (Armonk, NY: IBM Corp.) was used for statistical analysis. The continuous variables are summarised as mean \pm standard deviation. The differences between the groups were assessed using the Student's t-test and a Mann-Whitney U test for normally distributed and non-normally distributed data, respectively. Univariate analysis by Chi-square test was performed to test differences in proportions. Statistically significant results obtained from the univariate analysis were subjected to multivariate logistic regression. A p value <0.05 was considered to be statistically significant.

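### Time to identify the nerve is compared without covariates, although each lobe's ultrasound volume and BMI are recorded before surgery; the cost is precision and protection against chance imbalance, not validity

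*Protocol*

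**What the plan says.** **Outcome.** The Protocol's Study Design section lists, among the items recorded during surgery, the "period of time for initial identification of RLN after the mobilization of upper pole on each site". Later in the same section "period of time for RLN identification" is one of the many variables compared between group 1 (lateral) and group 2 (cranio-caudal). The primary endpoint is RLN injury. The secondary endpoints concern what influences that injury. Identification time is in neither list.

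**Covariates.** BMI appears in the same Study Design sentence as "evidence of autoimmune thyroid disease (ATD) and thyroid lobe volume were recorded in all patients, preoperatively". Volume is computed from the dimensions "of each thyroid lobe measured by ultrasonography according to the following formula", so it exists separately for each side.

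**Allocation.** Study Design describes assignment by the parity of a random number in a sealed envelope, opened on the morning of surgery. No stratification is described.

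**Analysis.** In the SAP, differences in continuous variables are "assessed using the Student's t-test and a Mann-Whitney U test for normally distributed and non-normally distributed data, respectively". The only multivariable step is this: "Statistically significant results obtained from the univariate analysis were subjected to multivariate logistic regression". A logistic model needs a binary outcome, so it cannot serve a time. Neither document contains a covariate-adjusted analysis of identification time.

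**The concern.** Identification time is the most direct measure in the plan of how readily each route finds the nerve. Its clock starts after upper-pole mobilisation, and under the Protocol's RLN identification heading both routes begin after the upper-pole vessels are ligated, so the arms are comparable on this measure.

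The size of the lobe and the patient's build could plausibly affect how long the search takes. If they do, a two-sample test leaves that variation in the error term and the interval is wider than it need be. A chance difference between arms in lobe volume or BMI would also shift the estimate, in proportion to how strongly the covariate is related to time. Both variables are already in the data, and volume is matched to the side on which the time is measured.

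The Protocol says that they were recorded preoperatively, not explicitly before randomisation. The dissection route cannot change either of them, so they remain proper baseline covariates.

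**Working it through.** **Inputs from the documents**
- Randomised: 121 lateral, 112 cranio-caudal. Excluded afterwards: 9 and 26. Analysed: 121 − 9 = 112 and 112 − 26 = 86, total 198.
- Sides: 158 total thyroidectomies and 40 lobectomies give up to 2 × 158 + 40 = 356 sides.
- Significance level 0.05, taken as two-sided.
- The plan gives no sample size, power, SD or covariate–outcome correlation, so there is no design figure to reproduce.

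**Assumption.** R² is the share of the variance of log time explained by lobe volume and BMI together. It is shown from 0 to 0.30.

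**1. Precision, patient as unit.** The unadjusted SE of the difference, in SD units, is √(1/112 + 1/86) = 0.143. The difference detectable with 80% power is (1.960 + 0.842) × 0.143 = 0.402 SD. Adjustment multiplies the variance by 1 − R². Power at 0.402 SD is then Φ(2.802/√(1 − R²) − 1.960).

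| R² | Variance ratio | SE ratio | Power at 0.402 SD | Unadjusted N of equal precision, 198/(1 − R²) |
|---|---|---|---|---|
| 0 | 1.00 | 1.00 | 80% | 198 |
| 0.10 | 0.90 | 0.95 | 84% | 220 |
| 0.20 | 0.80 | 0.89 | 88% | 248 |
| 0.30 | 0.70 | 0.84 | 92% | 283 |

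A simulation of the t-test against a linear model with two covariates (4,000 runs per setting) gave almost no loss at R² = 0: power 79.3% adjusted, 79.5% unadjusted.

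**2. Two sides per patient.** For the mean of two sides, let ρ be the between-side correlation of the covariate part and c that of the residual. The variance ratio is

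(1 − R²)(1 + c) / [(1 − R²)(1 + c) + R²(1 + ρ)].

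When ρ = c this is 1 − R². Two extremes (ρ and c assumed) show the spread:

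| R² | ρ = 0, c = 0.7 | ρ = c | ρ = 1, c = 0 |
|---|---|---|---|
| 0.10 | 0.94 | 0.90 | 0.82 |
| 0.20 | 0.87 | 0.80 | 0.67 |
| 0.30 | 0.80 | 0.70 | 0.54 |

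For the 40 patients with one side the ratio is 1 − R². A side-level simulation with about 80% of patients bilateral (3,000 runs, within-patient correlations assumed) gave 1.01, 0.88, 0.79 and 0.67 at R² = 0, 0.10, 0.20 and 0.30.

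**3. Chance imbalance.** The standardised difference in a covariate between arms of 112 and 86 has SD 0.143, so 95% of allocations fall within ±1.96 × 0.143 = ±0.28 SD. This assumes that the exclusions are unrelated to the covariate. At that limit, a covariate with correlation R to time shifts the unadjusted estimate by R × 0.28 SD:
- R = 0.3: 0.08 SD, or 0.59 SE.
- R = 0.5: 0.14 SD, or 0.98 SE.

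**4. Validity.** In the simulation with no true difference, the unadjusted t-test at patient level rejected in 4.9% to 5.2% of runs.

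**5. Why the model needs a patient term.** If the 356 sides were treated as independent, the design effect would be 1 + [(158 × 4 + 40)/356 − 1] × ICC = 1 + 0.888 × ICC. A nominal 5% test would run at about 8% at an assumed ICC of 0.3 and about 10% at 0.5. This is a separate matter from covariate adjustment, but any side-level model must deal with it.

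**The case against.** **Nothing in the test is invalid.** A reader might infer that the unadjusted comparison is biased. The documents do not support that on the ground of missing covariates. With intact randomisation, the patient-level test holds its error rate and its standard error already allows for chance imbalance. This stands: omitting covariates is a choice that costs efficiency.

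**Imbalance does not carry over in full.** A reader might suppose that a difference in lobe size passes straight into the time difference. It enters only after multiplication by the correlation, which the documents do not give. Thyroid volume and BMI are also on the list of compared variables, so a marked imbalance would be seen, though not corrected.

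**The trial's main conclusion is untouched.** This time is one item in a long list of compared variables. That stands and limits the weight of the point.

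**The gain is assumed.** That volume and BMI affect search time is a judgement, and no single percentage can be defended. This also stands, which is why the result is given as a range that includes zero.

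**It is late.** Both documents are dated 1 March 2020, use the past tense and report analysed counts for patients referred up to November 2019. A model added now cannot be presented as prespecified before data collection. That stands as a condition on how it is reported.

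**A larger imbalance threat exists.** Exclusions after randomisation were 9/121 (7.4%) against 26/112 (23.2%), Fisher p about 0.0009. Adjustment for two covariates would address any resulting imbalance only in part. This matters more than chance imbalance and should rank above it.

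**Conclusion.** The point holds as an optional improvement. Identification time is tested without covariates although two suitable ones, one of them specific to the side, are already recorded in all patients and the described allocation does not balance them. What is lost is precision and protection against chance imbalance.

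Under assumed explained variance of 0%, 10%, 20% or 30%, the variance of the arm difference would fall to about 1.0, 0.9, 0.8 or 0.7 of the unadjusted value. At 30% the ratio ranges from 0.80 to 0.54 across the extreme between-side correlations tried. If the covariates explain nothing, adjustment gains nothing and costs almost nothing.

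The result rests on an R² and on correlations that the documents do not contain. It does not bear on the RLN injury comparison.

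**What to change.** Add to the SAP a linear model for log identification time per side, with randomised approach, that side's log ultrasound lobe volume and BMI as fixed effects, and a patient random effect. Report the ratio of geometric means with its 95% interval. Keep the two-sample test as a supporting result.

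Name these two covariates in the SAP and keep them whatever their univariate p values; the selection rule written for the logistic model should not apply here. If the model is added after data collection, say so. State beside the result that it does not repair the unequal exclusions after randomisation.

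The cost is one SAP sentence and one extra model on data already collected. The small downside is an effect expressed as a ratio instead of a difference in minutes.
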